10.4. Other Efficacy Endpoints and Analyses

10.4.1. Other Efficacy Endpoint 1

The percentage of patients achieving complete corneal healing of PED or corneal ulcer at Week 8, defined as the greatest diameter of corneal fluorescein staining in the area of the PED or corneal ulcer < 0.5 mm as assessed by a central reader, will be summarised.

The analysis will be performed on the mITT population according to the estimand framework and ICE definitions of the binary secondary and other efficacy endpoints (Section 7.2) using the CMH test controlling for randomisation strata at Week 8. Missing data will be imputed as per Section 8.3.2. The same table output will be created as for the primary efficacy analysis.

10.4.2. Other Efficacy Endpoint 2

The percentage of patients achieving complete corneal healing of PED or corneal ulcer at Week 8, defined as the greatest diameter of corneal fluorescein staining in the area of the PED or corneal ulcer < 0.5 mm as assessed by the investigator, was summarised.

The analysis will be performed on the mITT population according to the estimand framework and ICE definitions of the binary secondary and other efficacy endpoints (Section 7.2) using the CMH test controlling for randomisation strata at Week 8. Missing data will be imputed as per Section 8.3.2. The same table output will be created as for the primary efficacy analysis.

10.4.3. Other Efficacy Endpoint 3

The percentage of patients achieving complete corneal clearing at Week 8, defined as a score of 0 using the Oxford scale, will be summarised.

The analysis will be performed on the mITT population according to the estimand framework ind ICE definitions of the binary secondary and other efficacy endpoints (Section 7.2) using the CMH test controlling for randomisation strata at Week 8. Missing data will be imputed as per Section 8.3.2. The same table output will be created as for the primary efficacy analysis. In addition the Oxford scale results are summised descriptively by frequency counts by visit based on observed data only.

10.4.4. Other Efficacy Endpoint 4

The time from treatment start to at least 50% corneal healing is defined as a \geq 50% reduction in the greatest diameter of the lesion as determined by a central reader in days. Treatment group and randomisation strata are used as covariates. Patients who do not achieve at least 50% corneal healing until end of treatment (V8/D56) are censored at date of V8/D56 or last available date if early terminated in case no intercurrent event (ICE) occurred. The censoring date after the occurrence of an ICE and respective imputation will be the actual assessment date at (V8/D56), if available. In case the patient has no efficacy assessment done at (V8/D56), the censoring time (days) after the ICE occurrence will be set to Day 56, which is the last scheduled efficacy assessment day in the 8 week treatment administration period as planned per protocol. The analysis will be performed on the mITT population according to the estimand framework and ICE definitions for the time to event endpoints (Section 7.2). Missing data will be imputed with single value imputation as per Section 8.3.2.

The HRs and their 95% Wald CIs and p-values, as well as the estimate and 95% CI for the median, 25% and 75% quartiles of time to at least 50% corneal healing, will be reported in a table; the survival probability for the treatment groups will be plotted in a figure.

10.4.5. Other Efficacy Endpoint 5

The time from treatment start to at least 50% corneal healing was defined as a \geq 50% reduction in the greatest diameter of the lesion as determined by the investigator in days. Treatment group and randomisation strata are used as covariates. Patients who do not achieve at least 50% corneal healing until end of treatment (V8/D56) are censored at date of V8/D56 or last available date if early terminated in case no intercurrent event (ICE) occurred. The censoring date after the occurrence of an ICE and respective imputation will be the actual assessment date at (V8/D56), if available. In case the patient has no efficacy assessment done at (V8/D56), the censoring time (days) after the ICE occurrence will be set to Day 56 which is the last scheduled efficacy assessment day in the 8 week treatment administration period as planned per protocol. The analysis will be performed on the mITT population according to the estimand framework and ICE definitions for the time to event endpoints (Section 7.2). Missing data will be imputed with single value imputation as per Section 8.3.2.

The HRs and their 95% Wald CIs and p-values, as well as the estimate and 95% CI for the median, 25% and 75% quartiles of time to at least 50% corneal healing, will be reported in a table; the survival probability for the treatment groups will be plotted in a figure.

10.4.6. Other Efficacy Endpoint 6

The time from treatment start to onset of healing was defined as a > 20% reduction in the greatest diameter of the lesion as determined by a central reader in days. Treatment group and randomisation strata are used as covariates. Patients who do not achieve > 20% reduction until end of treatment (V8/D56) are censored at date of V8/D56 or last available date if early terminated in case no intercurrent event (ICE) occurred. The censoring date after the occurrence of an ICE and respective imputation will be the actual assessment date at (V8/D56) if available. In case the patient has no efficacy assessment done at (V8/D56), the censoring time (days) after the ICE occurrence will be set to Day 56 which is the last scheduled efficacy assessment day in the 8 week treatment administration period as planned per protocol. The analysis will be performed on the mITT population according to the estimand framework and ICE definitions for the time to event endpoints (Section 7.2). Missing data will be imputed with single value imputation as per Section 8.3.2.

The HRs and their 95% Wald CIs and p-values, as well as the estimate and 95% CI for the median, 25% and 75% quartiles of time to onset of corneal healing, will be reported in a table; the survival probability for the treatment groups will be plotted in a figure.

10.4.7. Other Efficacy Endpoint 7

The time from treatment start to onset of healing was defined as a > 20% reduction in the greatest diameter of the lesion as determined by the investigator in days. Treatment group and randomisation strata are used as covariates. Patients who do not achieve > 20% reduction until end of treatment (V8/D56) are censored at date of V8/D56 or last available date if early terminated in case no intercurrent event (ICE) occurred. The censoring date after the occurrence of an ICE and respective imputation will be the actual assessment date at (V8/D56), if available. In case the patient has no efficacy assessment done at (V8/D56), the censoring time (days) after the ICE occurrence will be set to Day 56 which is the last scheduled efficacy assessment day in the 8 week treatment administration period as planned per protocol. The analysis will be performed on the mITT population according to the estimand framework and ICE definitions for the time to event endpoints (Section 7.2). Missing data will be imputed with single value imputation as per Section 8.3.2.

The HRs and their 95% Wald CIs and p-values, as well as the estimate and 95% CI for the median, 25% and 75% quartiles of time to onset of corneal healing, will be reported in a table; the survival probability for the treatment groups will be plotted in a figure.

10.5. Other Exploratory Endpoints and Analyses

10.5.1. Other Exploratory Endpoint 1

The change from baseline in QoL evaluated using the NEI VFQ-25 will be analyzed (Mangione at al. 2001). Scores for the NEI VFQ-25 will be calculated according to the NEI VFQ-25 scoring algorithm document, and the original responses captured in the CRF are recoded according to Table 8. The subscale scores are calculated as the arithmetic mean over the items available in each subscale (Table 9). The composite score is the arithmetic mean over all subscale scores excluding the general health item.

Responses for each item are converted to a scale from 0 to 100, with 0 representing the worst and 100 representing the best visual functioning.

Table 8: Recoding of item responses for calculation of subscale means

Item Numbers	Original Response Category	Recoded
1, 3, 4, 15c *	1	100
	2	75
	3	50
	4	25
	5	0
2	1	100
	2	80
	3	60
	4	40
	5	20
	6	0
5, 6, 7, 8, 9, 10, 11, 12, 13, 14, 16,	1	100
16a	2	75
	3	50
	4	25
	5	0
	6	Missing #
17, 18, 19, 20, 21, 22, 23, 24, 25	1	0
	2	25
	3	50
	4	75
	5	100

^{*:} Item 15c has four-response levels but is expanded to five-levels using item 15b. If 15b = 1 then recode to 15c = 0; if 15b = 2 then 15c = missing; if 15b = 3 then 15c = missing.

Table 9: Averaging items to generate subscale scores

Scale	Number of items	Items to be averaged (after recoding per Table 10)
General Vision	1	2
Ocular Pain	2	4, 19
Near Activities	3	5, 6, 7
Distance Activities	3	8, 9, 14

^{#:} The original response category 6 indicates problems that are not related to vision and therefore it is recoded as missing.

Sponsor: Recordati Rare Diseases; Protocol No.: REC0559-B-001

Vision Specific:			
Social Functioning	2	11, 13	
Mental Health	4	3, 21, 22, 25	
Role Difficulties	2	17, 18	
Dependency	3	20, 23, 24	
Driving	3	15c, 16, 16a	
Color Vision	1	12	
Peripheral Vision	1	10	

Mean scores per subscale are calculated based on non-missing answers devided by the total number of items with non-missing answers. The same is applicable for the composite score.

An ANCOVA will be performed for the change from baseline in composite score data at Week 8. The LSM estimates and 95% CIs of each treatment group, as well as the LSM differences, 95% CIs and p-values from the comparison between the REC 0/0559 groups and the vehicle group, will be reported. Missing values for the composite and subscale scores are imputed according to the estimand framework and definition of ICE of the continuous secondary and other exploratory efficacy endpoints (Section 7.2). Missing data will be imputed with MI as per Section 8.3.2. A summary table will present all values and changes from baseline in composite and subscale scores by visit and treatment group based on observed data only.

10.5.2. Other Exploratory Endpoint 2

The change from baseline in the overall NRS score for ocular symptoms and tolerability will be analyzed. The overall NRS score will be calculated as the arithmetic mean of individual symptoms scores. If more than 3 symptom scores are missing the overall NRS mean score will be set to missing for the respective visit.

An ANCOVA will be performed for the change from baseline in overall NRS score at Week 8. The LSM estimates and 95% CIs of each treatment group, as well as the LSM differences, 95% CIs and p-values from the comparison between the REC 0/0559 groups and vehicle group, will be reported. Missing values for the overall mean NRS score are are imputed according to the estimand framework and definition of ICE of the continuous secondary and other exploratory efficacy endpoints (Section 7.2). Missing data will be imputed with MI as per Section 8.3.2. A summary table will present all values and changes from baseline in each symptom score and overall score by visit and treatment group based on observed data only.

11. Analysis of Pharmacokinetics

The pharmacokinetics of MT6, the active metabolite of REC 0/0559, will be evaluated using an intense PK sampling schedule for the first 24 patients on Day 1 and Day 7. All randomised patients will have trough levels measured at Day 28 and Day 56. All outputs are presented for the patients in the PK population.

11.1. PK Sampling Schedule

Blood samples for the PK analysis of MT6 levels will be collected at the time points indicated below. The actual date and time of each blood sample collection will be recorded.

Day 1 and Day 7 (±1 day) PK sampling will be done for the first 24 patients only.

On Day 1 and Day 7 (±1 day), a predose PK sample will be obtained, and postdose PK samples will be obtained at 10, 20, and 40 minutes, and 1, 2, and 4 hours after the first daily REC 0/0559 administration (before the next REC 0/0559 administration), and at 20 minutes and 4 hours after the second daily REC 0/0559 administration.

On Day 28 (±2 days) and Day 56 (±3 days), trough PK sampling will be done for all patients at 4 hours postdose (before the next REC 0/0559 administration).

11.2. Plasma PK Parameters

For the first 24 patients:

- On Day 1 and Day 7: PK parameters of C_{max}, C_{max ss}, T_{max}, T_{max ss}, AUC₀₋₄ (Day 1), AUC_τ (Day 7) and AUC_{0-t} for the 1st daily administration using an intense PK collection schedule
- On Day 1 and Day 7: plasma levels at 20 minutes and 4 hours after the 2nd daily administration

C_{trough} for all patients:

• On Day 28 and Day 56: trough plasma levels at 4 hours postdose (before the next REC 0/0559 administration)

11.3. Presentation of Concentration Data

11.3.1. Handling of Missing Data

Missing concentration data for all patients who are administered scheduled study treatments will be considered as non-informative missing and will not be imputed. No concentration estimates will be provided for missing sample values.

For the derivation of AUC and for the individual plasma concentration versus time curves, the following rules will apply:

- On Day 1 and Day 7, all sample concentrations BLQ will be set to zero before the first measurable concentration, otherwise they will be set to missing
- The sampling time of pre-dose samples, collected before the first administration, relative to dosing will also be treated as zero

For plasma concentration summary, the following rules will apply:

- All BLQ values will be set to zero
- No further imputation will be applied to any missing values

11.3.2. Listing and Presentation of Individual PK Data

The actual and nominal sampling times of PK blood sample collection will be listed for each patient and will include the deviation in time from the protocol scheduled time (i.e., nominal time), if applicable.

All measured concentrations will be presented in original units as reported by the bioanalytical laboratory.

- Individual patient plasma concentration data will be listed by dosing regimen (dose level), patient, study visit and time point.
- Individual PK profiles on Day 1 and Day 7 will be presented by nominal times by dose level, if required by randomisation strata

11.3.3. Summary of PK Concentrations by Matrix

The summary of PK concentrations will be presented by dose level (cohort), by randomisation strata disease stage and region, by scheduled time points for each visit using the following descriptive statistics: n, number and % BLQ, arithmetic mean, SD, CV%, minimum, median, maximum.

11.4. PK Parameters Derivation

11.4.1. Handling of the No Reportable Concentration Values

Samples with invalid concentration (due to bioanalytical or clinical issue) will be replaced by "0.00" when it occurs prior to dosing. Otherwise they will be set to missing for tabulation, graphical representation and calculation purposes if it occurs after dosing.

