- Day 1 and Day 7 (±1 day) PK sampling will be done for the first 24 patients only. On Day 1 and Day 7 (±1 day), PK samples will be obtained predose, and postdose PK samples will be obtained at 10, 20, and 40 minutes, and 1, 2, and 4 hours after the first daily administration (but before the next administration). On Day 7 (±1 day), patients should be instructed not to take their first dose of study drug before the clinic visit, so that the predose PK sample can be obtained.
- Trough PK sampling will be done for all patients, at day 28 (±2 days), 4 hours postdose but before the next administration and at Day 56 (±3 days), 4 hours postdose. Patients should administer study drug before the clinic visit and record the time of study drug administration in the study drug diary, so that timing for the PK sampling can be determined.
- At visit 1b, provide patient with study drug diary and instruction how to fill it out.
- Visit 8 is the last day of study drug administration. After last study assessments belonging to Visit 8, no more study drug administration is allowed.

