11.4.2. Handling of the Difference between the Scheduled and the Actual Sampling Times

The actual clock time for dosing and each collection time for the PK samples will be recorded. For all sampling times, the actual sampling times relative to dosing will be calculated as the difference between the actual clock time of sampling and the actual clock time of dosing. The actual post-dose sampling times relative to dosing expressed in hours and rounded off to three decimal digits will be used to calculate the PK parameters, except for pre-dose samples occurring prior to dosing, which will always be reported as zero (0.000), regardless of the time difference. Scheduled sampling times will be presented in concentration tables individual and mean graphs.

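### SAP 11.4.1 enters 0.00 for an invalid pre-dose PK sample without limiting this to Day 1, so on Day 7 the zero is an invented value that would mask any overnight carry-over

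*SAP*

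**What the plan says.** SAP 11.4.1 has two branches for a concentration that is invalid for a bioanalytical or clinical reason. Before dosing, it "will be replaced by '0.00' when it occurs prior to dosing". After dosing the treatment is different: "Otherwise they will be set to missing for tabulation, graphical representation and calculation purposes if it occurs after dosing". Neither branch names a day or visit.

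SAP 11.1 puts a pre-dose sample on two days for the first 24 patients: "On Day 1 and Day 7 (±1 day), a predose PK sample will be obtained". For Day 7, Protocol Table 2 adds that "patients should be instructed not to take their first dose of study drug before the clinic visit", so the sample precedes that day's first drop but follows several days of treatment.

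Three neighbouring rules bear on the reading:

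- **SAP 11.3.1, missing concentrations:** they "will be considered as non-informative missing and will not be imputed".
- **SAP 11.3.1, sampling time:** "The sampling time of pre-dose samples, collected before the first administration, relative to dosing will also be treated as zero". Here the limit to the first dose is written out.
- **SAP 11.4.2, actual sampling times:** post-dose times are calculated from the clock, "except for pre-dose samples occurring prior to dosing, which will always be reported as zero (0.000), regardless of the time difference". Here the phrase covers pre-dose samples in general.

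For results below the limit of quantification (BLQ), 11.3.1 uses zero before the first measurable value on Day 1 and Day 7 when deriving AUC, and zero throughout for concentration summaries. The footnotes to Table 14.2.5.3 and Listing 16.2.5.2.2 use zero only for the Day 1 pre-dose sample and half the lower limit of quantification (LLOQ) after Day 1.

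**The concern.** Before the first administration on Day 1 the patient has had no drug, so entering zero for a spoiled sample adds a value known to be right. On Day 7 nobody knows the true value. A zero entered there can be correct or too low, never too high, so any error runs in one direction.

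The Day 7 pre-dose sample shows directly whether drug persists overnight, and it is the starting point of the Day 7 profile. The PK profile in the first 24 patients is part of a primary objective, Protocol 5.4 says no clinical trial of the drug had been done, and neither document gives a human half-life. Low carry-over is therefore an expectation that this sample helps to test, and a rule that can enter the expected answer as data weakens the test.

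**Working it through.** The plan gives no figure to reproduce here. The check has three parts.

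**1. Does the rule reach Day 7?** Section 11.4.1 names no day. Sampling (11.1) and parameter derivation (11.4.3) cover Days 1 and 7. Section 11.4.2 uses the same phrase for pre-dose samples generally. Section 11.3.1 restricts its sampling-time rule to before the first administration, and 11.4.1 has no such restriction. As written, the rule covers Day 7. Dosing before that sample spans Days 1 to 6, so 6 days, or 5 to 7 with the ±1 day window.

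**2. Effect on the Day 7 pre-dose summary.** SAP Table 2 gives 6 active patients per dose in Cohorts 1 to 3. Assume six equal, quantifiable true values and that the substituted zero enters the summary. With m zeros, reported mean / true mean = (6 − m)/6.

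- m = 1: 5/6 = 0.833, a fall of 16.7%.
- m = 2: 4/6 = 0.667, a fall of 33.3%.

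With five values of 1 and one of 0, the minimum is 0, the median stays at 1 and the CV is 49%. With the invalid value set to missing, n is 5 and the mean is not pulled down.

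**3. Effect on AUCtau.** Only the 0 to 10 minute segment uses the pre-dose value C0. Concentration rises there, so the linear trapezoid applies, and replacing C0 by zero removes C0 × (10/60 h)/2 = 0.083 h × C0.

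To size this, assume one compartment, instantaneous absorption and 24 equal doses (0, 4, 8 and 12 h on Days 1 to 6), with sampling at the planned Day 7 times. The overnight gap is then 12 h. With k = ln 2 / half-life, and in units of the single-dose peak, C0 = Σ exp(−k(144 − tᵢ)), where tᵢ are the dose times in hours. The human half-life is an assumption, shown over a range:

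| Half-life | C0 / observed Day 7 peak | Change in AUCtau with 0.00 |
|---|---|---|
| 10 min | about 0 | 0.00% |
| 30 min | about 8 × 10⁻⁸ | 0.00% |
| 2 h | 2.2% | −0.08% |
| 4 h | 20% | −0.57% |
| 6 h | 39% | −1.00% |
| 12 h | 67% | −1.55% |

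Hand check at 4 h: C0 = 0.238, so the loss is 0.238/12 = 0.0198. Against an AUCtau of 3.489 that is 0.57%.

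The effect therefore falls on the Day 7 pre-dose summary and the profile plots, and hardly at all on AUCtau.

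**The case against.** The strongest objection is that the practical effect is probably nil. Protocol 5.2.1 gives half-lives of about 30 and 10 minutes in rat and rabbit, so a 12 h gap is 24 to 72 half-lives. A valid sample would then be BLQ, and 11.3.1 would summarise it as zero anyway. This stands as an expectation, and it is why the masking must be stated conditionally. It does not justify entering the expectation as a result in a first trial with no human half-life.

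The phrase in 11.4.1 could also mean before the first dose ever. That is possible but not written. If it was intended, the fix simply states it.

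Four stronger inferences are tempting but lack support:

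- **That this sample is the only evidence on accumulation.** It is not. Day 7 AUCtau against Day 1 AUC0-4, Cmax,ss against Cmax, the 4-hour levels on both days and the Day 28 and Day 56 troughs all inform on it. Invalid post-dose samples go to missing.
- **That a sample drawn after a patient dosed at home would be reported as zero.** Such a sample was arguably taken after dosing, so the second branch of 11.4.1 would set it to missing. The SAP does not say that home dosing is a clinical issue in its sense.
- **That the 17% and 33% falls are certain.** The reference in 11.4.1 to tables, graphs and calculations is attached to the missing branch. The SAP does not say where the pre-dose 0.00 is used.
- **That 11.4.1 flatly contradicts 11.3.1.** One section covers missing concentrations and the other invalid ones. They overlap and fit poorly, and the SAP does not say which governs a spoiled Day 7 sample.

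Nor do safety decisions or inference depend on this rule. Protocol 13.2 sends exposures above 10 nM from the PK laboratory to the DMC by a separate route, and SAP 11.5 plans no statistical model for PK.

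**Conclusion.** The point holds as a minor error in a data-handling rule. Followed as written, 11.4.1 enters an invented zero for a patient who has been on treatment for about six days. That value can only lower the reported Day 7 pre-dose level, and it would mask overnight carry-over if there is any. It also fits poorly with the no-imputation rule in 11.3.1. Under the footnotes to Table 14.2.5.3 and Listing 16.2.5.2.2, a spoiled Day 7 sample would count for less than a valid BLQ one.

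The fall of 17% for one zero, or 33% for two, in the Day 7 pre-dose mean needs three conditions: true levels are quantifiable, they are about equal across the 6 patients, and the zero enters the summary. The AUCtau change of at most about 1.6% rests on the simple model and the assumed half-lives. If the true level is BLQ, the mean under 11.3.1 is unchanged. Efficacy analyses are not affected.

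**What to change.** In SAP 11.4.1:

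- Limit the 0.00 replacement to the Day 1 sample taken before the first administration.
- Set an invalid Day 7 pre-dose result to missing in tables, graphs and calculations.
- Report that patient's Day 7 AUCtau as not calculable, with a flag.

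Do not fill the gap with the 4-hour concentration. That value follows a 4 h gap, while the Day 7 pre-dose sample follows about 12 h. Under the same model, the 4-hour level relative to C0 is (1 + C0) × exp(−4k) / C0, which is about 12-fold at a half-life of 2 h, 2.6-fold at 4 h and 1.2-fold at 12 h. The substitution would replace a small downward error with an upward one.

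At the same time, reconcile the Day 7 BLQ rules in 11.3.1 with the footnotes to Table 14.2.5.3 and Listing 16.2.5.2.2.

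This takes a few lines of SAP text. The downside is that an occasional Day 7 pre-dose value or AUCtau will be missing, out of 6 active patients per dose.
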